## 7.6 Medical History

The study physician (or other qualified medical study staff) will conduct a complete medical history covering past and present conditions to help determine eligibility and to provide baseline information regarding medical conditions.

## 7.7 Clinic Visit Form (CV)

This form is filled out each time the participant is seen at the site, whether for a scheduled visit or for an extra (non-data) visit. Non-data visits may include visits simply to prescribe additional medication or to adjust medication dosage. It will not be filled out for TAU visits, such as psychosocial treatment sessions. At scheduled data visits, this form will be used to collect information regarding amount and type of psychosocial treatment since the last data visit, vital signs (including weight, oral temperature, blood pressure, pulse rate and respiration), pregnancy test results, self-reports and urine drug screen reports of illicit drug use, and prescription and dosing information. At non-data visits, only header information and prescription information (if applicable) will be completed.

#### 7.8 Induction Form

This form documents that inclusion/exclusion criteria have all been satisfied and that the day of induction falls within the appropriate time frame after consent. It is also used to document dropouts prior to induction (i.e. screen fails or no shows for induction). This form will be faxed to the coordinating center at UCLA when a participant is inducted. The coordinating center will fax back to the sites an attendance log, which delineates the appropriate dates for visits up to randomization day (Day 0).

Protocol # CTN-0003 Version 7C

#### 7.9 Risk Behavior Survey (RBS)

This is a brief, 12-item (with multiple sub-items) interviewer administered assessment of HIV risk behaviors including intravenous drug use and sexual risks. This survey will be utilized to assess degree of HIV-infection risk by looking at risk behavior. Measures will include extent and methods of past drug use, sexual preference, sexual history, and extent of unprotected sex; and assessment of travel to international locations of increased HIV-infection rates. This measure takes approximately 20 minutes to administer.

#### 7.10 Liver Function Tests (LFTs)

In addition to collection of liver functions tests (LFTs) at screening, LFTs (including AST, ALT, GGT, ALP, and Bilirubin) will be repeated every 4 weeks for all participants while receiving medication (regardless of Hepatitis B/C status). Specifically, LFTs will be collected, in addition to screening, on Study Day 0 and on study day 28 for all participants (with a 7 day window). Repeat LFTs will also be obtained upon early termination from the study if more than one month has passed since they were last assessed.

Laboratories performing any of the blood tests must either be directly regulated by CAP or CLIA or indirectly according to CLIA guidelines. All sites must provide normal values for their designated lab and proof that the lab is CLIA or CAP certified.

If AST, ALT, GGT, ALP collected at Day 0 or Day 28 are greater than 3 times the normal limit and these results represent an increase of more than 25% from the screening LFT or the total bilirubin is greater than 2.0 mg/dL or the participant has symptoms suggestive of liver toxicity (e.g. fever, extreme fatigue, dark urine, clay colored stools, jaundice), LFTs will be repeated as clinically indicated and at a frequency of not less than every 2 weeks until results are reliably decreasing or stable. If a participant has worsening symptoms or LFTs continue to increase (AST, ALT, or GGT>500 IU or Bilirubin>3.0 mg/dL), physicians should handle the situation as clinically indicated and are strongly encouraged to consult with the study Medical Monitor and/or a hepatologist. All referrals and consultations are to be clearly noted in medical progress notes.

#### 7.11 Physical Exam (PHY)

The study physician (or other qualified medical study staff) will complete a physical exam to help determine eligibility, to ensure that there are no medical concerns regarding participation and to gather baseline information regarding the participant's physical health. The physical exam will be repeated at the 1 Month Post Taper Follow-Up and at early termination if more than one month has passed since last assessed.

#### 7.12 Hematology/Chemistries/Hepatitis

Complete blood counts (CBC) with differentials and platelet count and a standard Blood Chemistry Panel (BC) will be performed to help determine eligibility at screening.

Protocol # CTN-0003

Version 7C

Date of Preparation: 1/31/05

Page 26 of 44

Hematologic tests will also be repeated at the 1 Month Post Taper Follow-Up visit or upon early termination from the study if more than one month has passed since they were last assessed. At screening, Hepatitis B and C serologies will be conducted including Hepatitis B surface antigen (HBs Ag), Hepatitis B core IGM antibody (Anti-HBc) and Hepatitis C virus antibody (HCV Ab).

Laboratories performing any of the blood tests must either be directly regulated by CAP or CLIA or indirectly according to CLIA guidelines. All sites must provide normal values for their designated lab and proof that the lab is CLIA or CAP certified.

## 7.13 Routine Urinalysis (UA)

Standard urinalysis will be performed to help determine eligibility at screening. Urinalysis will also be repeated at the 1 Month Post Taper Follow-Up visit or upon early termination from the study if more than one month has passed since the last assessment. Each site will be asked to provide normal values from the lab conducting the urinalysis for their site and proof that the lab is certified.

## 7.14 12-Lead Electrocardiogram (ECG)

Participants over the age of 40, or those under the age of 40 with a history of cardiovascular disease, will be administered 12-lead ECGs at screening and at the1 month post taper follow-up visit. Repeat ECGs should also be obtained on participants (with screening ECGs) who terminate early from the study if more than one month has passed since the last ECG was performed. In order to standardize collection of ECGs across site and ensure ECGs are collected and interpreted in the same manner, the Pacific Node will subcontract with Covance Central Diagnostics for the collection and interpretation of ECGs at each participating CTP throughout the CTN. Covance Central Diagnostics will provide equipment, training, toll free transmission, interpretation and hard copy reports using the MTX-2 telephonic transmission device. The portable MTX-2 permits digital data acquisition, onboard storage, and remote transmission and interpretation and yields high quality ECGs. Reports are received within two hours of ECG collection to facilitate faster inclusion/exclusion decisions and participant care.

## 7.15 Pregnancy Testing (PG)

Female participants will be required to have a negative pregnancy test (PG) prior to induction and monthly thereafter while receiving Suboxone. Buprenorphine is a Pregnancy Category C Drug. Female participants will also be expected to practice acceptable birth control. Women who become pregnant any time prior to day 7 or 28 (depending on randomization group assignment) will be withdrawn from the study and given immediate access to methadone maintenance services at the CTP or another local treatment provider. Participants refusing methadone maintenance will be referred to another local provider, preferably one providing specialized services for pregnant or post-

Protocol # CTN-0003 Version 7C

partum women. Results of the pregnancy test performed every 4 weeks (Days - 42, -28, 0, 28), will be recorded on the Clinic Visit CRF.

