**Table 1: Time and Event Schedule** 

	Table 1: Time and Event Schedule																		
STUDY DAY/MEASURE	-42	-28	-25	-21	-14	-7	0	7	14	21	28	35	42	49	56	84	91	112	TERM
Informed Consent	X																		
Treatment Contract/Suboxone		W 7																	
Information Sheet	•	X																	
Locator Form	X																		
Demographics	X																		
DSM-IV Checklist	X																		
Clinical/Psychiatric Interview	X																		
Inclusion/Exclusion	X																		
Medical History	X																		
Clinic Visit Form (CV)	X	X	X	X	X	X	X	X	X	X	X	X	X	X	X	X	1	2	X
Induction Form		X																	
RBS	X											1			2		1	2	$X^3$
LFTs	X						X				X								$X^3$
Physical Exam (PHY)	X											1			2				$X^3$
Hematology/Chemistries/Hepatitis												4							3
Routine Urinalysis	X											1**			2**				X** 
12-lead ECG	X *											1*			2*				X*3
Pregnancy Test (PG)	X	X					X				X								$\mathbf{X}^3$
Adverse Events (AE)	X	X	X	X	X	X	X	X	X	X	X	X	X	X	X	X			X
Prior/Concomitant Medications	$\mathbf{X}^{\mathbf{P}}$	X	X	X	X	X	X	X	X	X	X	X	X	X	X	X			X
Randomization Form							X												
COWS	X	X	X	X	X	X	X	X	X	X	X	X	X	X	X	X	1	2	X
ARSW	X	X	X	X	X	X	X	X	X	X	X	X	X	X	X	X	1	2	X
ASI Lite	X											1			2		1	2	$X^3$
VAS	X	X	X	X	X	X	X	X	X	X	X	X	X	X	X	X	1	2	X
STR																	1	2	X
SQ								1			2	1			2		1	2	X
Urine Drug Screen (U)	X	X	X	X	X	X	X	X	X	X	X	X	X	X	X	X	1	2	X
Dosing Log (DL)			X	X	X	X	X	X	2	2	2								
Serious Adverse Event (SAE)																	1	2	X
` '	X=All Participants																		

X=All Participants

Term=If a participant terminates from the protocol at any time post induction and prior to the one month post-taper follow-up visit, he/she should complete data collection as indicated

Protocol # CTN-0003

Page 8 of 44

Version 7C

1=Participants assigned to the 7 day tapering

2=Participants assigned to the 28 day tapering

\*For Participants over age 40 or with a history of cardiovascular disease.

P=Prior Med Form Only

\*\* Hepatitis Tests not repeated (done only at screening)

<sup>3=Complete only if one month or more has passed since previous assessment

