#### Group 1:

```
Day 8: End of Taper Visit (CV, AE, CM, COWS, ARSW, VAS, SQ, U, DL)
(3 day window - post)

Day 14: Weekly Visit (CV, AE, CM, COWS, ARSW, VAS, U)

Day 21: Weekly Visit (CV, AE, CM, COWS, ARSW, VAS, U)

Day 28: 1 Month Post Randomization Follow-Up
(CV, LFT, PG, AE, CM, COWS, ARSW, VAS, U)

Day 35: 1 Month Post Taper Follow-Up (7 day window - post)
(CV, RBS, PHY, BC, UA, ECG, AE, CM, COWS, ARSW, ASI, VAS, SQ, U)

Day 42: Weekly Visit (CV, AE, CM, COWS, ARSW, VAS, U)

Day 49: Weekly Visit (CV, AE, CM, COWS, ARSW, VAS, U)

Day 56: Weekly Visit (CV, AE, CM, COWS, ARSW, VAS, U)
```

Protocol # CTN-0003 Version 7C

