#### Group 2:

```
Day 29: End of Taper Visit and 1 Month Post Randomization Follow-Up (CV, LFT, PG, AE, CM, COWS, ARSW, VAS, SQ, U, DL) (3 day window - post)

Day 35: Weekly Visit (CV, AE, CM, COWS, ARSW, VAS, U)

Day 42: Weekly Visit (CV, AE, CM, COWS, ARSW, VAS, U)

Day 49: Weekly Visit (CV, AE, CM, COWS, ARSW, VAS, U)

Day 56: 1 Month Post Taper Follow-Up (7 day window - post) (CV, RBS, PHY, BC, UA, ECG, AE, CM, COWS, ARSW, ASI, VAS, SQ, U)
```

It should be noted that the total number of visits during stabilization, taper, post taper and follow-up are the same for both groups (however, they occur in different phases, that is group 2 has more taper visits while group 1 has more post taper visits, but the total is identical).

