#### 4.11 Post Study Options/Early Termination

Upon completion of the tapering phase, or in cases of early dropout, participants may continue in TAU at the CTP or may be referred to available local treatment resources. In the event any participant desires additional pharmacological treatment for their opiate

Protocol # CTN-0003

Version 7C

dependence or if the study staff finds that additional treatment is clinically indicated, the site will refer the participant to a local provider of methadone, LAAM, or buprenorphine. Participants enrolled in Treatment As Usual (TAU), usually psychosocial treatment, at the site will be encouraged to continue participation once the taper is complete, if they have not completed this treatment. Any participant who has completed TAU and desires further psychosocial treatment will be given a referral to a local treatment provider. Treatment received after the taper is complete, either pharmacological or psychosocial will not exclude the subject from further participation in this research protocol. Involvement in additional treatment(s) will be noted in the data and participation in this study will continue as outlined. In case of early drop out, a termination visit will be scheduled and all measures as indicated in the "term" column of the Time and Event schedule should be completed.

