#### **9.2 Outcome Measures**

#### Primary Outcome Measure

In keeping with this hypothesis, there is one primary outcome, the proportion of participants providing opiate free urines in each group on the day following the end of the taper. This outcome will be evaluated at the end of the taper. It will also be evaluated at 1 and 3 months post completion of tapering.

Secondary Outcome Measure

Several secondary outcomes will be evaluated. These include:

- 1. Comparison of number of opiate free participants by stabilization dose and taper schedule.
- 2. Comparison of:
  - a. The number of opiate free urine specimens at follow-up
  - b. The number of all drug free urine specimens at follow-up
  - c. Frequency of concomitant medication used to treat withdrawal symptoms
  - d. Severity of withdrawal symptoms as assessed by COWS and ARSW
  - e. The mean VAS craving level of each group
  - f. The mean SQ score (participant satisfaction) of each group
  - g. The number and severity of adverse event

These measures will be analyzed within a time course framework. We will compute change from baseline to follow-up in measures taken only at those timepoints (ASI). For measures collected repeatedly throughout the taper schedule (COWS, ARSW, SQ, concomitant meds, adverse events), we will plot the pattern of responses by group over time.

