#### 9.3 Intent-to-Treat and Evaluable Populations

The main intent-to-treat population is defined as the participants who are randomized to a tapering schedule at the end of the 28 day induction and stabilization. The evaluable participant population is defined as participants who are randomized and who complete the tapering schedule without being administratively withdrawn. Parallel analyses will be conducted on these two populations, and their results compared, to assess the impact of completion status on the results.

Protocol # CTN-0003 Version 7C

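### Section 7.15 ends all follow-up, not only Suboxone, for a woman who becomes pregnant before the end of her taper, although she stays in the intent-to-treat population; the effect is small and cheap to avoid

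*Protocol*

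**What the plan says.** Protocol 7.15 sets the window as "Women who become pregnant any time prior to day 7 or 28 (depending on randomization group assignment") and says that these women "will be withdrawn from the study and given immediate access to methadone maintenance services at the CTP or another local treatment provider". Pregnancy tests are listed for Days -42, -28, 0 and 28.

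The primary outcome (9.2) is "the proportion of participants providing opiate free urines in each group on the day following the end of the taper". It is to be evaluated again at 1 and 3 months after the taper. Section 4.9 places the primary visit at "Day 8: End of Taper Visit (CV, AE, CM, COWS, ARSW, VAS, SQ, U, DL") in the 7-day arm, with a urine screen but no pregnancy test. In the 28-day arm it is "Day 29: End of Taper Visit and 1 Month Post Randomization Follow-Up", where the pregnancy test and the urine screen are taken together. Both visits may be held up to three days late.

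On the analysis set, 9.3 states: "The main intent-to-treat population is defined as the participants who are randomized to a tapering schedule".

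On leaving early, 4.11 states: "In case of early drop out, a termination visit will be scheduled and all measures as indicated". The termination column of Table 1 applies when "a participant terminates from the protocol at any time post induction and prior to the one month post-taper follow-up visit", and it includes a urine screen, AEs and SAEs.

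Section 4.7 treats stopping drug and leaving the study as separate acts. A 28-day-arm participant who misses a week of medication is not restarted, but may keep attending and is still active for study activities and analysis. The same section ends both drug and participation when a change in medical status makes continuing unsafe. Section 4.11 lets participants who take up other treatment after the taper, including methadone, stay in the study.

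**The concern.** Pregnancy is a good reason to stop a taper of study drug and to move the woman to suitable care. It is not in itself a reason to stop collecting her urines, scales and safety data. A randomized woman withdrawn under 7.15 still counts in the intent-to-treat population but contributes nothing after her exit visit. An analysis plan cannot recover visits that were never held.

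At stake are her 1- and 3-month post-taper results, the scheduled AE and SAE collection during a pregnancy that began around drug exposure, and in some cases her primary urine. Because the rule runs to the end of each taper, it covers a longer period in the 28-day arm, so any loss while on drug would tend to be uneven between arms.

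**Working it through.** **1. When can the rule act?** Inputs: tests on Days -42, -28, 0 and 28 (7.15); last dose on Day 7 or Day 28 (4.6); primary urine on Day 8 or Day 29 (4.9).

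- A positive result read on Day 0 before randomization costs no randomized data, because 4.5 allows her to be replaced.
- 7-day arm: the next scheduled test is Day 28. That is 28 - 8 = 20 days after the primary urine and 28 - 7 = 21 days after the last dose.
- 28-day arm: the next scheduled test is at the Day 29 visit, the same visit as the primary urine and one day after the last dose.

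No test is scheduled between Day 0 and the primary urine in either arm.

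**2. Two readings of the window.** The text can refer to when the pregnancy began or to when it was found.

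- *By when it began:* a taper-period pregnancy found by the Day 28/29 test triggers withdrawal after dosing has ended. The primary urine is kept.
- *By when it was found:* the Day 28/29 test falls outside the window, so after randomization the rule acts only on a pregnancy found between scheduled tests while she is on drug. The primary urine then lies ahead of her. It is lost unless the termination visit happens to fall in Days 8-11 or 29-32.

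**3. Loss per woman found at Day 28/29.**

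- Visits cancelled: Days 35, 42, 49, 56, 84, and 91 or 112 = 6.
- Scheduled AE collection (to Day 84, 8.6): 84 - 28 = 56 days (7-day arm); 84 - 29 = 55 days (28-day arm).
- Urine and SAE follow-up (to Day 91 or 112): 91 - 28 = 63 days; 112 - 29 = 83 days.

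**4. Loss per woman found on drug between tests.** Each arm has 10 scheduled visits after Day 0.

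- 7-day arm, found Days 1-6: all 10 visits; AE collection 84 - 6 = 78 to 84 - 1 = 83 days; urine and SAE follow-up 91 - 6 = 85 to 91 - 1 = 90 days.
- 28-day arm, found Days 1-27: 10 visits down to 7 (after the Day 21 visit); AE collection 84 - 27 = 57 to 84 - 1 = 83 days; urine and SAE follow-up 112 - 27 = 85 to 112 - 1 = 111 days.
- Window length: 6 versus 27 days, a ratio of 27/6 = 4.5 (28/7 = 4 if the last dosing day is counted).

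**5. How many women?** The protocol gives neither the share of women nor a pregnancy rate. Assume 30-40% women and 0.5-3% conceiving per 28 days:

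- 28-day arm: 240 × 0.30 × 0.005 = 0.36 to 240 × 0.40 × 0.03 = 2.88.
- 7-day arm (× 7/28): 0.09 to 0.72.

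**6. Effect on the primary comparison.** First the plan's own power (9.6): 20% versus 32%, two-sided 5%, 240 per group, stated as about 82%, and 72% with 20% dropout (240 × 0.8 = 192). The continuity-corrected normal formula is Φ[(d - 1/n - 1.96·SE0)/SE1].

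- At n = 240: SE0 = √(2 × 0.26 × 0.74/240) = 0.0400 and SE1 = √((0.16 + 0.2176)/240) = 0.0397, giving 82.7%.
- At n = 192 it gives 72.9%. The plan's figures are reproduced.
- Without the correction, the values are 85.2% and 76.6%.

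Now an upper-end illustration: three women in the 28-day arm, every one found on drug between tests, so that every primary urine is lost.

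- Share of the arm: 3/240 = 1.25%. At the same daily rate the 7-day arm has 3/4.5 = 0.67 women, or 0.28%.
- If missing counts as not opiate free and all would have been opiate free: 1.25 - 0.28 = 0.97 points.
- At the planning rates: 1.25 × 0.32 - 0.28 × 0.20 = 0.34 points.
- Uncorrected power, with three lost from the 28-day arm only: 85.2% falls to 85.0% if they are simply missing. It falls to 83.0% if they count as not opiate free (0.32 × 237/240 = 0.316).

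With detection by scheduled test only, the effect on the primary comparison is nil.

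**The case against.** The strongest case is that withdrawal is a legitimate choice. Pregnancy is an exclusion criterion (3.3). Section 4.7 joins unsafe medical status to both drug stop and withdrawal. A woman moved to methadone maintenance is on the opposite course from a taper, so her later urines would reflect that treatment. Section 4.11 tolerates other treatment only once the taper is complete. The provision in 4.7 for those who miss a week rests partly on their having already reached zero dose. All of this stands as a reason not to call 7.15 an error. It does not show that the visits have to end, and 7.15 gives no reason why they should.

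Three stronger readings are tempting, and the documents do not support them.

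- *A reader might infer that the primary urine is usually lost.* The test schedule says otherwise: a scheduled test comes at or after that urine in both arms. The longer window in the 28-day arm therefore bears on the primary result only through unscheduled detection.
- *A reader might infer that her safety data are lost altogether.* Existing AEs are followed to resolution (8.6), SAEs that staff learn of within one year after study completion are reported (7.27), and the termination visit records AEs and SAEs. What stops is the scheduled collection of new events.
- *A reader might infer a contradiction with 4.7.* There is none. Section 4.7 shows only that the protocol can keep someone off drug in follow-up, and its medical-status clause points the same way as 7.15.

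**Conclusion.** The point holds as a modest improvement. Section 7.15 orders study withdrawal where stopping drug would do, and leaves a randomized woman in the intent-to-treat population without later data. The clearest case is a taper-period pregnancy found at the Day 28/29 visit: withdrawal then prevents no exposure and cancels six visits. Loss of the primary urine is confined to pregnancies found between scheduled tests while on drug.

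The effect on the primary comparison is negligible to small: nil under scheduled detection, and under 1 percentage point of the 12-point target in the three-woman illustration. That illustration rests on an assumed number of women, unscheduled detection of every case and missing urines counted as not opiate free. The protocol fixes none of these. That ending visits is unnecessary is an inference from 4.7 and 4.11; the protocol does not say it about pregnancy.

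**What to change.** In 7.15, change the consequence from withdrawal from the study to discontinuation of study medication, and keep the methadone or specialist referral as it is. Add two sentences: that she may continue all remaining scheduled visits as an active participant, as 4.7 already provides for others, unless she withdraws consent; and that pregnancy alone does not trigger the medical-status withdrawal in 4.7. Record any methadone start on the existing Concomitant Medication Form (7.17, kept through Day 84), so that later urines can be read alongside it.

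The cost is an IRB amendment under 8.1 and any matching consent wording. No new visit or form is needed. Some women may decline to continue, and urines after a methadone start will reflect that treatment.
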